### **5.3.9.3 Exploratory Efficacy analysis**

PFS will be summarized by exon 19 and 21 as median time and will be estimated through Kaplan-Meier method.

### **5.3.10 Safety analysis**

Safety endpoints will be presented considering the safety population.

### **5.3.10.1 Drug dispensing and accountability**

During the treatment period, the number of patients whose study medication was dispensed will be evaluated together with the frequency of patients starting the study with doses of 150mg, 100mg or 50mg, the median (range) duration of study drug dispensability, and the mean (SD)/median (range) number of respective units (tablets) dispensed. Moreover, the percentage of patients who kept the same initial dose until the end of study treatment and who had to change dose will be calculated as well as the mean of the weighted average doses of each patient (the weights being the time a patient was on each dose).

At the end of study treatment, the mean (SD) compliance ratio for each patient will be derived, and the respective percentage of compliant patients assessed. Furthermore, a patient will be deemed compliant if the compliance ratio is at least 80%.

### **5.3.10.2 Physical examination**

The absolute (n) and relative (%) frequencies of patients who perform a physical examination at each visit will be evaluated. The frequency of abnormal results in the examination of the skin, nails, thorax, abdomen, extremities, head, genital, neurological, temperature or other physical examination will be described.

### **5.3.10.3 ECG**

The absolute (n) and relative (%) frequencies of patients who perform an ECG at the screening visit, and every time that is clinically indicated will be described, as well as the frequency of abnormal clinically relevant ECGs results for each visit and for total study duration.

### **5.3.10.4 Laboratory data**

Laboratory assessment will be carried out at the screening visit and all visits during the treatment period. For the following laboratory parameters:

- 1) Hematology (hemoglobin, leucocytes, neutrophils, platelets),
- 2) Coagulation (prothrombin time, activated partial thromboplastin (aPTT), international normalized ratio (INR – only at the screening visit) and
- 3) Biochemistry (urea, glucose, AST, ALT, creatinine clearance (if indicated), serum creatinine, calcium, sodium, potassium, chloride, LDH, alkaline phosphatase, total bilirubin)

the percentage of patients with abnormal clinically relevant values will be assessed.

Laboratory will be summarized in shift from baseline tables.

### **5.3.10.5 Adverse events**

Adverse event (AE) data will be presented in frequency tables (overall, by grade (1, 2, 3, 4, or 5), by severity (mild, moderate, severe, life threatening or disabling or death related), by relationship (unrelated, remote relation, possible relation or probable relation) and by action taken (dose changed, interrupted, withdrawal or none). In tables showing the incidence of adverse events, subjects who experienced the same event on more than one occasion are counted only once in the calculation of the event frequency.

For selected events of particular interest, such as Stevens-Johnson syndrome and interstitial lung disease, summary tables will be presented for time to first onset of the event and for the total number of episodes. Every occurrence of an event in any subject will be counted in the total number of episodes but successive reports of an identical event in the same phase (treatment, follow-up) will be combined (concatenated) into a one episode if the end date of the earlier event was the same as the start date of the later event, or if the end date of the earlier event was missing.

A listing of adverse events by patient, whose adverse events led to withdrawal of study treatment or to dose modification will be done. In case of deaths, a brief narrative describing each death will be done.

All AEs and laboratory variables will be assessed according to the NCI CTC-AE version 4.0 grading system.

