7.1.2 Drug – Adverse Event relationship

The causality relationship of study drug to the adverse event will be assessed by the investigator as either:

Yes or No

If there is a reasonable suspected causal relationship to the study medication, i.e. there are facts (evidence) or arguments to suggest a causal relationship, drug-event relationship should be assessed as **Yes**.

The following criteria should be considered in order to assess the relationship as **Yes**:

- Reasonable temporal association with drug administration
- It may or may not have been produced by the subject's clinical state, environmental or toxic factors, or other modes of therapy administered to the subject.

- Known response pattern to suspected drug
- Disappears or decreases on cessation or reduction in dose

The following criteria should be considered in order to assess the relationship as **No**:

- It does not follow a reasonable temporal sequence from administration of the drug.
- It may readily have been produced by the subject's clinical state, environmental or toxic factors, or other modes of therapy administered to the subject.
- It does not follow a known pattern of response to the suspected drug.
- It does not reappear or worsen when the drug is re-administered.

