7.1.5 Treatment and Follow-Up of AEs

The final outcome of each AE must be recorded on the eCRF. All AEs will be followed up according to the guidelines below:

Related AEs

Continue to follow up until one of the outcomes listed below is reached:

- Resolved or improved to baseline.
- Relationship is reassessed as unrelated.
- Death.
- Start of new anti-cancer regimen.
- Investigator confirms that no further improvement can be expected.
- Clinical or safety data will no longer be collected or final database closure.

Unrelated severe or life threatening AEs

Continue to follow up until one of the outcomes listed below is reached:

- Resolved or improved to baseline.
- Severity improved to Grade 2.
- Death.

- Start of new anti-cancer regimen.
- Investigator confirms that no further improvement can be expected.
- Clinical or safety data will no longer be collected or final database closure.

Unrelated Grade 1 or Grade 2 AEs:

To be followed up until one of the outcomes listed below is reached:

- Resolved or improved to baseline.
- Start of a new anti-cancer regimen.
- Investigator confirms that no further improvement can be expected.
- Clinical or safety data will no longer be collected or final database closure.

The final outcome of each adverse event must be recorded on the eCRF.

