**Table 28 – Adverse events and serious adverse events – Safety population**

	Total (n=xx)
Patients with at least one adverse event, n (%)a)	
No	
Yes	
Total	
Patients with at least one serious adverse event, n (%)a)	
Yes	
No	
Total	
Patients with at least one adverse event of special interest, n (%)a)	
Stevens-Johnson Syndrom	
Interstitial Lung Disease	
Grade of adverse events, n (%)b)	
Grade 1	
Grade 2	
Grade 3	
Grade 4	
Grade 5	
Total	
Severity of adverse events, n (%)b)	
Mild	
Moderate	
Severe	
Life threatening or disabling	
Death related	
Total	
Relationship of study drug, n (%)b)	
Unrelated	
Remote relation	
Possible relation	
Probable relation	
Total	
Action taken for adverse event, n (%)b)	
Dose increased	
Dose not changed	
Dose reduced	
Drug interrupted	
Drug withdrawn	
Not applicable	
Unknown	
Serious adverse events, n (%)b)	
Yes	
No	
Outcome, n (%)b)	
Not recovered / Not resolve	
Recovering / Resolving	
Recovered / Resolved	
Recovered / Resolved with sequelae	
Fatal	
Unknown	

a) Percentage calculated within the total number of patients of safety population (n=xx).

b) Percentage calculated within the total number of adverse events reported by safety population (n=xxx).

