**Table 30 – Incidence of serious adverse events – Safety population**

	Total (n=xx)
Incidence of serious adverse events, n (%)	
Body system 1	
Xxxxx	
Xxxxx	
Xxxxx	
Body system 2	
Xxxxx	
Xxxxx	
Xxxxx	

a) Percentage calculated for total of patients of patients of the safety population (n=xx).

**Table 31** – Incidence of adverse events with remote, possible or probable relationship with study drug – Safety population

	Total (n=xx)
Incidence of adverse events with remote, possible or probable relationship with study drug, n (%)	
Body system 1	
Xxxxx	
Xxxxx	
Xxxxx	
Body system 2	
Xxxxx	
Xxxxx	
Xxxxx	

a) Percentage calculated for total of patients of patients of the safety population (n=xx).

**Table 32** – Incidence of serious adverse events with remote, possible or probable relationship with study drug – Safety population

	Total (n=xx)
Incidence of serious adverse events with remote, possible or probable relationship with study drug, n (%)	
Body system 1	
Xxxxx	
Xxxxx	
Xxxxx	
Body system 2	
Xxxxx	
Xxxxx	
Xxxxx	

a) Percentage calculated for total of patients of patients of the safety population (n=xx).

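### Does the mismatch between Yes/No causality in the protocol and graded causality in the SAP leave the related-AE tables undefined?

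*SAP*

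**What the plan says.** Protocol 7.1.2 sets a two-way judgement. The sentence "The causality relationship of study drug to the adverse event will be assessed by the investigator as either" leads to Yes or No, with criteria for each. Yes applies "If there is a reasonable suspected causal relationship to the study medication". One criterion for Yes begins "It may or may not have been produced by the" and goes on to the patient's clinical state, environment or other therapy. Its counterpart under No begins "It may readily have been produced by the" and names the same sources. Protocol 7.1.5 also works with two classes: it separates related from unrelated events for follow-up, and one way to end follow-up of a related event is "Relationship is reassessed as unrelated".

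The SAP uses a graded scale. Section 5.3.10.5 presents adverse events "by relationship (unrelated, remote relation, possible relation or probable relation", and Table 28 has a block headed "Relationship of study drug, n" (%) with those four levels as rows. Table 31 is titled "Incidence of adverse events with remote, possible or probable relationship with study drug". Tables 32, 35 and 36 use the same pool of three levels, as do SAP 5.5 and Protocol 8.2.7 for the interim analysis. The protocol is therefore out of step with itself as well as with the SAP.

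SAP 5.3 says that Appendix 3 describes all derived variables. Appendix 3 has none for relatedness, and neither document equates Yes with any set of graded levels.

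**The concern.** Safety is a secondary objective. Protocol 8.1.4 and SAP 3.3.3 both promise the incidence of erlotinib-related SAEs and non-SAEs, and Tables 31, 32, 35 and 36 deliver it. If the form records only Yes or No, the SAP asks for categories that nobody collected. If it records four levels, the protocol describes an assessment that was not the one made, and events rated remote are counted as related although 7.1.2 asks for a reasonable suspicion. The paired criteria in 7.1.2 do not say on which side a remote event falls. Undefined, that boundary could be drawn after the events have been seen, in a single-arm trial with no control rate to lean on.

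**Working it through.** There is no plan figure to reproduce. The check is to count the outputs that depend on relationship, then see whether each can be produced under either possible form.

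**1. Outputs that use relationship**
- The AE tables are 28 to 38, so 38 − 28 + 1 = 11. Those built wholly on the pooled group are 31, 32, 35 and 36: 4 of 11.
- Table 28 has nine blocks: any AE, any SAE, special-interest events, grade, severity, relationship, action taken, seriousness and outcome. One of the nine concerns relationship.
- SAP 6.12 lists Tables 29 to 34, 36 and 39 for the interim. Table 39 is subsequent therapy, which leaves 7 AE tables. Three of these (31, 32, 36) use the pooled group. Table 28 is not among them.

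**2. If the form holds Yes/No**
- The pooled titles cover every level except unrelated. With two recorded values, the only counterpart is pooled group = Yes and unrelated = No.
- Tables 31, 32, 35 and 36 can then be filled completely. Only their labels differ from what was collected.
- The relationship block of Table 28 has four rows for two recorded values. No fills the unrelated row and Yes can fill at most one other, so at least 4 − 2 = 2 rows stay empty. This is the only content that cannot be completed as laid out, and none of it is in the interim.

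**3. If the form holds four levels**
- Table 28 fills row by row. The titles of Tables 31, 32, 35 and 36 name the levels to be pooled, so a programmer needs no further definition.
- What remains is that Protocol 7.1.2 describes a coarser judgement than the one recorded.
- The related/unrelated split in Protocol 7.1.5 fits this branch too: unrelated is the bottom level and the other three lie above it.

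**4. Does the place of remote events open a choice?**
- With Yes/No data there is no remote category to move. With four levels the titles place it in the pool. Leaving it out would mean departing from the SAP.
- Including it can only raise a related-event count or leave it unchanged, so the stated rule does not hide drug-related events.
- In a term row of Table 31, a patient whose only occurrences of that term were rated remote adds 1/30 = 3.3 percentage points, assuming all 30 planned patients are treated. The documents give no number of such patients. The comparison is also with a definition excluding remote events, which neither document adopts, so this is not an error in the plan's result. Tables 35 and 36 use events as the denominator, so 1/30 does not apply there.

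**5. What does not depend on relationship**
- Tables 29, 30, 33 and 34 are all-causality. ORR, PFS, OS and the sample size do not use relationship, and Protocol 8.2.2 sets no hypothesis test. Under Protocol 7.2.1, events up to 28 days after the last dose are reported whatever the relationship.

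**The case for a change.** The strongest case is that investigator attribution is the only planned means here of separating drug effects from disease, so the threshold for related should be stated and not inferred from table titles. The wording of 7.1.2 really is silent on remote events. On either branch some text is wrong: the SAP's categories or the protocol's description of the assessment. One look at the form would show which.

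Most of this stands as a description. The texts conflict, the word related in Protocol 8.1.4 and SAP 3.3.3 is not defined, and the lack of an Appendix 3 entry is a gap. It is also true that Table 28 does not let a reader remove remote events from patient-level incidence: its relationship percentages are of events (footnote b) and are not split by seriousness. Listing 4 does allow it. It prints patient, event, relationship and seriousness for every adverse event, and with about 30 patients a regrouping can be done by hand.

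The step from gap to harm does not stand. Each branch leaves one natural reading, so there is no real latitude to draw the boundary after seeing the data. There are also hints that the SAP follows the form. SAP 5.3.9.2 notes that the first-dose date is not on the CRF, so its authors had looked at what the CRF captures, and the action and outcome rows of Table 28 read like form pick-lists. These are suggestive only.

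**Conclusion.** This is a minor inconsistency between documents, and no change to the plan follows. The worst case is one block of one table that cannot be completed as laid out, plus four tables whose titles name categories finer than those recorded. The other case is four tables that run exactly as titled and a protocol paragraph that describes the judgement too coarsely. In both, the analyst with the eCRF in hand reaches the related-event counts without a discretionary step.

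The conclusion rests on two assumptions: that the form uses one of the two scales in the documents, and that the pooled titles mean what they say, namely that anything not rated unrelated counts as related. The documents do not show which scale was collected. They show no effect on any endpoint, count or conclusion of this descriptive trial.

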### **5.3.11 Subsequent therapy for NSCLC**

In the safety follow-up and off-study visits, the frequency of patients who continue treatment for NSCLC with subsequent therapies will be assessed. For the patients taking subsequent therapies, the therapeutic line and treatment will be further described using absolute (n) and relative (%) frequencies. Results on subsequent therapy for NSCLC will be presented considering the safety population.

## **5.4 MISSING DATA**

Incomplete dates will be handled as stated in Appendix 4. All other missing values will be individually omitted from the analyses.

## 5.5 INTERIM ANALYSES

Interim analysis will include the following descriptive analyses:

Characterization - demographics, medical history, Eastern cooperative oncology group performance status, clinical response (RECIST criteria).

Efficacy – Best Overall response, progression free survival, overall survival and epidermal growth factor receptor. Additionally, PFS will be obtained for Exon 19 and Exon 20 (if applicable).

Safety – Drug compliance, adverse events (incidence of AE and SAE, incidence of AE and SAE with remote, possible or probable relationship with study drug, description of AE and SAE, SAE with remote, possible or probable relationship with study drug) and subsequent therapy for NSCLC.

Interim analysis will be conducted following the methodology/assumptions considered in section 5.3.

## 6 STATISTICAL TABLES

### 6.1 PATIENT DISPOSITION

Patient disposition will be presented as described in **Table 1** of Appendix 6.

### 6.2 DEMOGRAPHICS

Demographic characteristics will be presented as described in **Table 2** of Appendix 6.

### 6.3 CHILDBEARING POTENTIAL/PREGNANCY TEST

Results of the childbearing potential/pregnancy test will be presented as described in **Table 3** of Appendix 6.

### 6.4 MEDICAL HISTORY

Results on medical history will be presented as described in **Table 4** and **Table 5** of Appendix 6.

By-patient listing of co-morbidities will be presented in **Listing 1** of Appendix 7.

### 6.5 ECOG PERFORMANCE STATUS

ECOG performance status data will be presented in **Table 6** of Appendix 6.

By-patient listing of ECOG results will be presented in **Listing 2** of Appendix 7.

### 6.6 CONCOMITANT MEDICATIONS

Concomitant medications will be presented in **Table 7** of Appendix 6.

By-patient listing of concomitant medications will be presented in **Listing 3** of Appendix 7.

## 6.7 TUMOUR ASSESSMENT

Results of tumour assessment will be presented as described in **Table 8** of Appendix 6.

## 6.8 CLINICAL RESPONSE (RECIST CRITERIA)

Results of the clinical response according RECIST criteria will be presented in **Table 9** of Appendix 6.

## 6.9 EFFICACY ANALYSIS

### 6.9.1 Primary Efficacy analysis

Results of the primary efficacy analysis will be presented for ITT population in **Table 10** of Appendix 6 and PP population in **Table 11** of Appendix 6.

### 6.9.2 Secondary Efficacy analysis

Results of the secondary efficacy analysis will be presented in, **Table 12** to **Table 19** of Appendix 6 and in **Figure 2** to **Figure 4**.

*[Insert figure]*

**Figure 2** – Kaplan-Meier curve for progression free survival – ITT population

*[Insert figure]*

**Figure 3** – Kaplan-Meier curve for overall survival – ITT population

*[Insert figure]*

**Figure 4** – Kaplan-Meier curve for response duration – ITT population

### **6.9.3 Exploratory Efficacy analysis**

Results of progression free survival by exon 19 and 21 will be presented in **Table 20** and **Table 21** of Appendix 6 and in **Figure 5**.

*[Insert figure]*

**Figure 5** – Kaplan-Meier curve for progression free survival by exon 19 and 21 – ITT population

## **6.10 SAFETY ANALYSIS**

### **6.10.1 Drug dispensing and accountability**

Results on the drug administration will be presented in **Table 22** of Appendix 6.

### **6.10.2 Physical examination**

Physical exam findings will be presented in **Table 23** of Appendix 6.

### **6.10.3 ECG**

Electrocardiogram findings will be presented in **Table 24** of Appendix 6.

#### **6.10.4 Laboratory data**

Hematology, coagulation, biochemistry results will be presented in **Table 25**, **Table 26** and **Table 27**, respectively, of Appendix 6.

#### **6.10.5 Adverse events**

Adverse events will be described in **Table 28** to **Table 38** of Appendix 6.

By-patient listing with data about adverse events will be presented in **Listing 4** of Appendix 7.

### **6.11 SUBSEQUENT THERAPY FOR NSCLC**

Results on subsequent therapy for NSCLC will be present in **Table 39** of Appendix 6.

### **6.12 INTERIM ANALYSIS**

The interim analysis will include the analyses described in the following sections: 6.2 Demographics, 6.4 Medical history, 6.5 ECOG performance status, 6.8 Clinical response (RECIST criteria), 6.9 Efficacy analysis, 6.10.1 Drug dispensing and accountability (only reduction in starting dose and compliance) and 6.10.5 Adverse events (Table 29 to Table 34, Table 36 and Table 39).

---

# Appendix 1: Protocol Synopsis

## SINOPSES OF AIMS PROTOCOL NUMBER: ML25434

TITLE	Phase II, open-label study of erlotinib (Tarceva®) treatment in patients with locally advanced or metastatic non-small cell lung cancer who present activating mutations in the tyrosine kinase domain of the epidermal growth factor receptor.		
SPONSOR	Roche Farmacêutica Química, Lda	CLINICAL PHASE	II
INDICATION	Locally advanced or metastatic non-small cell lung cancer (NSCLC).		
OBJECTIVES	
Primary:
 
Objective response rate (ORR) of erlotinib (Tarceva®; 150 mg) in patients with locally advanced or metastatic stage non-small-cell lung cancer (NSCLC), who have not received previous chemotherapy for their disease and who present activating mutations in the tyrosine kinase (TK) domain of the epidermal growth factor receptor (EGFR).
 
Secondary:
 
 
• Progression-free survival (PFS),
 
• Overall survival (OS),
 
• Safety profile,
 
• Evaluate the EGFR mutation frequency in the study population
 
		
TRIAL DESIGN	Open-label, multi-centre Phase II study.		
NUMBER OF PATIENTS	30 patients		
TARGET POPULATION	Patients with histologically or cytologically confirmed locally advanced or metastatic NSCLC who have not received previous chemotherapy for their disease and who present activating mutations in the TK domain of the EGFR.		
INCLUSION CRITERIA	
 
1. Patients able and willing to give written informed consent. Consent must be obtained prior to any study-specific procedure.
 
2. 
 
a) Histologically or cytologically documented inoperable, locally advanced or metastatic NSCLC disease;
 
b) Patient that presents activating mutations in the tyrosine kinase domain of EGFR (Exon 19 deletion and/or exon 21 substitution L858R);
 
 
 
3. Measurable disease, according to RECIST - Response Evaluation Criteria in Solid Tumours).
 
4. Male or female patients aged ≥ 18 years.
 
5. Life expectancy ≥ 12 weeks.
 
6. Adequate haematological and coagulation function as assessed by the investigator.
 
		

	
 
7. Adequate liver and renal function as assessed by the investigator.
 
8. Female patients must be postmenopausal (24 months of amenorrhea), surgically sterile or they must agree to use a physical method of contraception. Male patients must be surgically sterile or agree to use a barrier method of contraception. Male and female patients must use effective contraception during the study and for a period of 90 days following the last administration of erlotinib. Acceptable methods of contraception include an established hormonal therapy or intrauterine device for females, and the use of a barrier contraceptive (i.e. diaphragm or condoms) with spermicidal.
 
9. If applicable, patients with asymptomatic and stable cerebral metastases receiving medical treatment will be eligible for the study. Those patients may have received radiation therapy for their cerebral metastases before the initiation of systemic treatment for non-small-cell lung cancer.
 
 
Able to comply with the required protocol and follow-up procedures

EXCLUSION CRITERIA	
 
1. Previous treatment with chemotherapy or therapy against EGFR, either with antibody or small molecule (tyrosine kinase inhibitor) for metastatic disease. The administration of neo-adjuvant or adjuvant therapy is allowed as long as it has finalized <math>\geq 6</math> months before entering the study. Patients can have received radiotherapy as long as the irradiated lesion is not the only target lesion for evaluating response and as long as radiotherapy has been completed before initiating the study treatment (28 days period is recommended). Treatment with an investigational drug agent during the four weeks before enrolment in the study.
 
2. History of another neoplasm other than carcinoma in situ of the uterine cervix, basal cell skin carcinoma treated adequately, or prostate carcinoma with a good prognosis (Gleason <math>\leq 6</math>) treated radically. History of another neoplasm treated curatively and without evidence of disease in the last 5 years. History of breast cancer and melanoma at any time.
 
3. Patients with symptomatic cerebral metastases.
 
4. Known hypersensitivity to erlotinib or any of its excipients.
 

	
 
5. Any significant ophthalmologic abnormality, especially severe dry eye syndrome, keratoconjunctivitis sicca, Sjögren's syndrome, severe exposure keratitis or any other disorder likely to increase the risk of corneal epithelial lesions. (The use of contact lenses is not recommended during the study. The decision to continue to wear contact lenses should be discussed with the patient's treating oncologist and the ophthalmologist.)
 
6. Use of coumarins (Sintrom®; Varfine®). If the patient requires anti-coagulant therapy, instead of coumarins, the use of a low molecular weight heparin is recommended, whenever clinically possible.
 
7. Patients with severe hepatic and renal impairment as assessed by the investigator.
 
8. Evidence of any other disease, neurological or metabolic dysfunction, physical examination or laboratory finding giving reasonable suspicion of a disease or condition that contraindicates the use of an investigational drug or puts the patient at high risk for treatment-related complications.
 
9. 
 
a) Positive urine pregnancy test in women of childbearing potential. Female patients should not be pregnant or breast-feeding.
 
b) Patients (male or female) with reproductive potential not willing to use effective method of contraception during the trial and during 90 days after the last erlotinib administration. Oral or injectable contraceptive agents cannot be the sole method of contraception.
 
 
 
10. Patients with pre-existing disease of the lung parenchyma such as lung fibrosis, lymphangitic carcinomatosis.
 
11. Patients with known infection with HIV, HBV, HCV. Testing is not required in the absence of clinical signs and symptoms suggestive of these conditions.
 
12. Patients those in the Investigator's opinion are not able to accomplish protocol requirements.
 
 
Incapacity to take oral medication or previous surgical procedures that affect absorption and imply the need for intravenous or parenteral feeding.

LENGTH OF STUDY	This study is event-driven, with a recruitment period that will last until the end of March 2012 or until the number of patients aimed for the protocol (30) is achieved, whatever occurs first. Patients are to be treated until disease progression, unacceptable toxicity, death or patient request for discontinuation.
END OF STUDY	The study will end when the last patient has stopped erlotinib therapy and completed their last safety follow-up visit (28 days after last study drug administration). For all

	patients who have discontinued study drug treatment and are alive, information on survival will be collected.
INVESTIGATIONAL MEDICINAL PRODUCT(S) DOSE/ ROUTE/ REGIMEN	Patients will be dosed daily with 150 mg erlotinib taken orally until disease progression or unacceptable toxicity. Dose reduction will be allowed according to protocol (Section 6.)
ASSESSMENTS OF:  - EFFICACY          - SAFETY          - EGFR Mutation analysis	
Primary Endpoint:
 
 
Objective Response Rate (ORR).
 
 
Secondary Endpoints:
 
 
Progression Free Survival,
 
Overall Survival (OS),
 
Safety profile,
 
EGFR mutation frequency.
 
 
All evaluations will be performed accordingly with the Schedule of Assessments. If clinically indicated, more evaluations could be performed. All adverse events (AEs) will be assessed using the National Cancer Institute Common Terminology Criteria for AEs (NCI CTC-AE) version 4.0. The incidence of serious adverse events (SAEs) and non-SAEs related to erlotinib therapy will be determined. Additional information about AEs of special interest (serious and non-serious) such as Stevens-Johnson syndrome and interstitial lung disease (IDL)-like events will be collected. Information about laboratory exams (haematology, biochemistry and coagulation), ECG and physical examination will be also collected.
 
If patients are deemed eligible to participate in the study by the investigator, a surgical fragment or biopsy formalin-fixed, paraffin-embedded or a tumour material obtained through aspiration cytology fixed and paraffin-embedded in a cell-block, must be sent to the Central Laboratory [REDACTED]. If activating mutations (exons 19 and/or 21 mutations) in the TK domain of EGFR gene are identified, patients are eligible to participate in the study.

STATISTICAL CONSIDERATIONS  - STATISTICAL METHODS	
Efficacy Analyses:
 
The primary and secondary efficacy analyses will be performed on the intent-to-treat population, defined as all subjects who are enrolled to the treatment phase of the study, regardless if they completed treatment. For ORR 95% confidence interval will be estimated. PFS and OS will be estimated and presented as median time to PFS and OS through Kaplan-Meier method. 95% confidence intervals will be estimated for this parameters. EGFR expression will be presented as a percentage and 95% confidence intervals will be estimated for this value.

- SAMPLE SIZE CONSIDERATION
	
Safety Analyses:
 
All safety parameters will be summarized and presented in tables based on the safety population.
 
AE data will be presented in standard frequency tables (overall and by intensity) by body system. All AEs and laboratory variables will be assessed according to the NCI CTC-AE version 4.0 grading system.
 
The sample size was calculated based on the primary variable of the study, objective response rate. Since this proportion is unknown an exploratory sample size of 30 patients was considered to evaluate primary endpoint. This sample size will allow estimating ORR with a margin of error of approximately <math>\pm 17.5\%</math>, for a 95% confidence interval.
 
Furthermore, approximately 2000 new cases of stage IIIB and IV NSCLC are diagnosed per year in Portugal and, based on published data, expected prevalence of EGFR mutation is approximately 10%. With a 95% confidence interval, it was calculated that at least 420 patients will have to be enrolled to be tested to achieve 30 positive cases for the exploratory sample size analysis.

------------------------------------	---

